Study Title: A Pilot Study to Evaluate Impact on Neurological Side Effects (Cognition, Memory, and Tremor) in Elderly (Age>65) Patients

NCT03461445

Date: November 21, 2018

1) Protocol Title

Title: Evaluating the difference in neurocognitive side effects between tacrolimus IR vs Envarsus XR ® in elderly renal transplant recipients.

Protocol Version Date: 11/21/18

2) Objectives

Primary objective: Change in neurocognitive side effects

Secondary Objectives: Change in self-reported side effects, Tacrolimus dose over concentration ratio, Graft survival, Patient survival

Null Hypothesis: Elderly patients will not experience a reduction in neurocognitive side effects when transitioned to Envarsus XR [®] when compared to elderly patients maintained on tacrolimus IR therapy.

3) Background

Renal transplant is widely accepted as the superior treatment for end stage renal disease in terms of mortality, morbidity, healthcare cost and quality of life¹. Elderly patients (>65 years) also benefit from transplantation. Studies have been conducted to evaluate the quality of life that elderly transplant recipient's experience. These studies have demonstrated that in appropriate recipients, quality of life is improved post-transplant². However, the medications required to prevent graft rejection come with toxicities that elderly patients may be more uniquely sensitive to.

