- 7. Nonadherence, as determined by a trough level less than 7 ng/mL after achieving therapeutic level with no other rationale for sub-therapeutic levels.
- 8. Adults unable to consent
- 9. Pregnant women
- 10. Prisoners

5) Study Timelines

Expected date of data collection and analysis completion by July 2019.

The duration of an individual subject's participation in the study is 6-8 weeks from initial study enrollment.

The enrollment period is expected to occur from IRB approval through December 2018, or until 60 subjects have been enrolled into to the study.

6) Study Endpoints

Primary Endpoints: Change in neurocognitive side effects assessed by MOCA scale, Digit symbol substitution test and tremor assessment scale.

[figure not shown]
Secondary Endpoints: Change in self-reported side effects, tacrolimus dose over concentration ratio, graft survival and patient survival.

Page :

7) Procedures Involved

Single-center, prospective, open-label, randomized study to evaluate the difference in neurocognitive side effects of Envarsus versus immediate release tacrolimus.

Figure 1. Flow diagram of study design

Enrollment:

- 1. Rolling enrollment of patients 65 years or older that fit the inclusion criteria outlined above
- 2. Plan to enroll 30 patients to each arm
- 3. Anticipated enrollment rate:
 - a. 6-8 patients in first month
 - b. 10 patients per month thereafter
 - c. Until total of 60 patients have enrolled
 - d. If any patients were to withdraw or be dropped from the study prior to completion of follow up testing, we will try to enroll more patients to replace them

Protocol:

- 1. Potential study participants will be screened within 4 weeks after transplantation.
 - Patients who meet study criteria will be consented and enrolled by 8 weeks posttransplantation
- Patients who consent to the study will be administered a baseline panel of neurocognitive tests.
 (Of note, these tests are not regularly administered to our post-transplant patients and are not part of the standard of care.)

Page 4

- Tests include: the MOCA, digit symbol substitution test, tremor assessment.
- They will also answer a side effects questionnaire.
- These tests will be performed in the mornings, between 1-4 hours after patients' morning tacrolimus dose administration.
- 3. Subjects who enroll will then be randomized to either remain on IR tacrolimus (current standard of care) or be converted to Envarsus.

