 - Those randomized to Envarsus will begin conversion immediately based on a dosing ratio of 0.8 x the total 24-hour IR tacrolimus dose that will lead to therapeutic tacrolimus trough levels.
 - Therapeutic drug level monitoring and will occur as per usual standard of care for all patients.
 - Blood draws for all subjects will occur as per usual standard of care and will be managed as per usual by the patients' post-transplant team.
 - Envarsus to be supplied by the pharmaceutical company.
 - IR tacrolimus to be supplied by patient's insurance
 - Any applicable vital signs or labs if collected as patient's standard of care may be used during the study period for study purposes.
- 4. Subjects' tacrolimus levels will be monitored and titrated as per usual practice at our center.
 - The target tacrolimus trough is 8-14ng/mL for patients within the first 3 months of transplantation.
 - They will obtain labs per standard of care (weekly) or at provider discretion.
 - Tacrolimus dose adjustment will be made per clinical judgement and expected to reach target goal range within 2 blood draws one week apart. (Total of two weeks).
- 5. 6 weeks after study enrollment (+/- 5 days), subjects will be administered the same panel of neurocognitive testing and self-reported questionnaires as at baseline.
 - The tests will be performed in the mornings, between 1-4 hours after patients' morning tacrolimus dose administration.
 - At this appointment the patients will receive a \$20 check to help with travel expenses for additional appointments.
- 6. After this study period, subjects who were randomized into the Envarsus arm will be given the option to remain on Envarsus or return to IR tacrolimus. Those who remain on Envarsus will be part of the extension phase of this study. The funding for the patients' Envarsus at this phase would revert back to their insurance coverage, with potential for coverage by Veloxis if further study will be completed (see below).
- 7. The extension phase of this study will create a cohort for the assessment of long term graft and patient outcomes.
 - We anticipate that if sufficient numbers plan to remain on Envarsus, we can apply for further funding for this phase. If further funding is approved, we will seek another IRB approval for continuation of this study.

 We do not anticipate long-term data to be collected about subjects beyond their period of participation in this study.

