encrypted online data management system (REDCap) using password protected computers. Due to the nature of the study, we will need to include patient identifiers in the database in order to assess adverse events for the duration of the study. The data will be stored until 1 year after publication of the study.

Data analysis plan: We will compare the neurocognitive scores between the Envarsus and IR Tacrolimus arms of the study. Sample size calcuation was done to determine sample size needed to detect a 1 point difference for each neurocognitive test we plan to use. The two groups will be compared using two-sample mean comparison via t test.

We will not be collecting or banking any patient specimens for this study.

9) Data and/or Specimen Banking

Participant data will be stored for potential future use by the PI and co-PIs pending further IRB approval. Data will only be released upon approval of PI with IRB approval. Data will be stored on encrypted devices requiring password protection. Passwords will not be shared by any users. Paper records of patient testing will be stored in locked cabinets with access only by research staff.

10) Provisions to Monitor the Data to Ensure the Safety of Subjects

Data will be extracted from the EMR and stored in a password protected folder on a secure, encrypted network. This network is only accessible by staff at UC Davis Health. This password protected folder will only be authorized to be accessed by study personnel. When this data is removed from this folder such as for the purposes of data analysis, each patient's data will be coded with a de-identified number. The identified patient information stored in the protected file will be destroyed at the end of this study.

For the duration of a subject's participation in the study, their clinical events and laboratory values will be monitored for any adverse events, including acute rejection, surgical complication, infections, cardiovascular events, neurologic events, and other events or side effects that may potentially be related to IR tacrolimus or Envarsus therapy. These data will be reviewed by the PI and co-PIs to determine if they are the direct result of use of the investigational drug.

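### The efficacy t test is not tied to the change endpoint and leaves the MOCA and DSS baselines out as covariates; ANCOVA would use them at no extra cost

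*Combined protocol and SAP*

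**What the plan says.** Section 2 states "Primary objective: Change in neurocognitive side effects", and section 6 repeats it: "Primary Endpoints: Change in neurocognitive side effects assessed by MOCA scale", together with the DSS test and a tremor scale.

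Section 7 sets the order of events. "Patients who consent to the study will be administered a baseline panel of neurocognitive tests" comes first. Randomisation follows: "Subjects who enroll will then be randomized to either remain on IR tacrolimus" or convert to Envarsus. Six weeks after enrolment, "subjects will be administered the same panel of neurocognitive testing and self-reported questionnaires as at baseline". MOCA and DSS baselines therefore exist for every randomised patient and cannot have been affected by the assigned treatment.

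The efficacy analysis is in the data analysis plan in section 8: "We will compare the neurocognitive scores between the Envarsus and IR Tacrolimus arms of the study", a mention of a sample size calculation for a 1-point difference on each test, and "The two groups will be compared using two-sample mean comparison via t test". No section says which score enters the t test, and none names a covariate.

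Section 7 also lists the tremor assessment among the baseline tests ("Tests include: the MOCA, digit symbol substitution test, tremor assessment"), yet describes its two components, PGI and CGI, as 7-point scales of tremor change.

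**The concern.** Two things are open or left unused.

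- **The tested variable.** Because the objective and endpoint are change, a t test of change is the natural reading. The analysis sentence speaks only of scores, so a t test of the 6-week score also fits it. In an open-label trial that choice should be fixed in advance. If both tests were run under the null and the better one reported, the false-positive rate would be about 9% to 10% instead of 5% (simulation, 30 per arm, equal SDs, correlation 0.3 to 0.8).
- **The baseline.** A t test of the 6-week score ignores it. A t test of change subtracts it, which fixes the baseline slope at 1. When the true slope is below 1, subtraction costs precision and over-corrects a chance imbalance. ANCOVA estimates the slope, and its adjusted arm difference is the same whether the outcome is the 6-week score or the change.

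At stake are the width of the interval around a 1-point effect and how far a chance baseline difference moves the result.

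**Working it through.** **Inputs from the protocol.** 30 per arm (section 7, Enrollment) and a 1-point difference (section 8). No SD, power, efficacy alpha, sidedness or correlation is given.

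**The plan's own figure.** The 30 per arm can be neither confirmed nor refuted. Back-solving with two-sided 0.05 and 80% power gives SD = 1 / [√(2/30) × (1.960 + 0.842)] = 1.38.

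**Assumptions.** Two-sided 0.05; the same SDs and correlation in both arms; a linear relation with a roughly normal baseline; 30 completers per arm; baseline to week-6 correlation r = 0.3, 0.5, 0.7, 0.8. Let k = week-6 SD / baseline SD, taken as 0.8, 1 and 1.25. Equal SDs are not guaranteed, since MOCA version 7.1 is used at Day 0 and 7.2 at 6 weeks.

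**Per-patient variances**, with S the week-6 SD:
- 6-week score: S²
- change: S² + (S/k)² − 2r·S·(S/k)
- ANCOVA: S²(1 − r²), multiplied by 1 + 1/56 = 1.018 for estimating the slope with 60 patients

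Hence ANCOVA/change = k²(1 − r²) / (1 + k² − 2kr), which is (1 + r)/2 when k = 1. ANCOVA/6-week = 1 − r² for any k. After the 1.018 factor, the worst case for ANCOVA is 1.018: against change when kr = 1, and against the 6-week score when r = 0.

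**Worked cell (S = 3, k = 1, r = 0.7).** Change: 9 + 9 − 2 × 0.7 × 9 = 5.40. ANCOVA: 9 × 0.51 × 1.018 = 4.67. Ratio 0.865. Power from the noncentral t (58 and 57 degrees of freedom): 37% and 42%.

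**All cells, week-6 SD 3:**

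| k | r | slope kr | variance ratio, large sample | ratio at 30 per arm | power, change | power, ANCOVA |
|---|---|---|---|---|---|---|
| 0.8 | 0.3 | 0.24 | 0.502 | 0.511 | 15.6% | 26.1% |
| 0.8 | 0.5 | 0.40 | 0.571 | 0.582 | 19.8% | 30.6% |
| 0.8 | 0.7 | 0.56 | 0.628 | 0.639 | 29.1% | 42.1% |
| 0.8 | 0.8 | 0.64 | 0.640 | 0.651 | 39.5% | 55.4% |
| 1 | 0.3 | 0.30 | 0.650 | 0.662 | 18.9% | 26.1% |
| 1 | 0.5 | 0.50 | 0.750 | 0.763 | 24.6% | 30.6% |
| 1 | 0.7 | 0.70 | 0.850 | 0.865 | 37.4% | 42.1% |
| 1 | 0.8 | 0.80 | 0.900 | 0.916 | 51.9% | 55.4% |
| 1.25 | 0.3 | 0.375 | 0.784 | 0.798 | 21.8% | 26.1% |
| 1.25 | 0.5 | 0.625 | 0.893 | 0.909 | 28.3% | 30.6% |
| 1.25 | 0.7 | 0.875 | 0.981 | 0.998 | 42.1% | 42.1% |
| 1.25 | 0.8 | 1.00 | 1.000 | 1.018 | 56.2% | 55.4% |

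Simulation of each cell (40,000 trials) agreed within 0.006 for power and 0.007 for the ratio. The t test of the 6-week score has 25% power at every r.

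**Other SDs, k = 1, r = 0.3 / 0.5 / 0.7 / 0.8:**
- SD 2: change 36 / 48 / 69 / 85%; ANCOVA 51 / 59 / 75 / 88%; 6-week score 48%
- SD 4: change 13 / 16 / 23 / 33%; ANCOVA 17 / 19 / 26 / 35%; 6-week score 16%

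**Chance imbalance.** The SE of the baseline arm difference is SD × √(2/30) = 0.516, 0.775, 1.033 at baseline SD 2, 3, 4. The probability of a difference above 1 point, the whole effect sought, is 5%, 20%, 33%. Each point of baseline difference moves the change comparison by kr − 1: −0.3 at k = 1 and r = 0.7, and −0.76 to 0 over the table.

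**The case against.** The strongest reply is that nothing here is an error. Sections 2, 6 and 7 together make a t test of change the obvious reading, and a change score already handles baseline, with a fixed coefficient. In a pilot, choosing between two valid tests could be called preference. That stands in part: there is no bias, and the ambiguity alone amounts to a missing cross-reference. It does not remove the point, because the fixed slope of 1 is an untested assumption that the collected data would let the analysis avoid.

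The second reply is that every size above rests on assumed inputs. That is correct, and the grid matters. At r = 0.9, SD 3 and equal SDs, the gain falls to 1.3 points (81.0% to 82.3%); at k = 0.8 it rises to 20 points. At the back-solved SD of 1.38 with equal SDs, power goes from 79% to 88% at r = 0.5 but only from 99.2% to 99.5% at r = 0.8. One SD grid also serves both MOCA and DSS, although a point need not mean the same on each. The direction is steadier than the size: ANCOVA loses only near kr = 1 (or against the 6-week score, near r = 0), and then by about 2% of variance under the stated assumptions. Fewer completers would raise that cost slightly.

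Third, section 11 mentions full-analysis and per-protocol sets, and no set is assigned to this test. That is a separate gap. ANCOVA needs the same two measurements per patient as a change score, so it loses no one whom the change test keeps.

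**Conclusion.** The point holds. The stated test is valid but is not linked to the change endpoint, and it leaves a usually more precise analysis of existing data unused. Against a change-score t test with equal SDs, ANCOVA reduces variance by about 8% to 34% for r = 0.8 down to 0.3. Against a 6-week-score test the gain grows with r: at SD 3 and r = 0.8, 25% power becomes 55%. Confidence is high on the wording gap and on the direction; the size depends on SDs and correlations that the protocol does not give. At SD 3, ANCOVA still reaches only 26% to 55% power over r = 0.3 to 0.8, so it does not solve low power. The change should be made, but the trial's validity does not depend on it.

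**What to change.** Replace the t test sentence in section 8 with wording such as:

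> For MOCA and DSS, the 6-week score is compared between arms by ANCOVA with the baseline score of the same test as covariate. The adjusted arm difference, which is identical for the 6-week score and the change, is reported with its 95% confidence interval. The unadjusted t test of change is supportive. PGI and CGI rate change directly, so their 6-week ratings are compared between arms by the two-sample t test without baseline adjustment.

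In section 7, reconcile the listing of the tremor assessment in the baseline panel with the description of PGI and CGI as change scales. If a different tremor measure is meant at baseline, the last sentence above would need to follow it.

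The cost is a short replacement text and one clarification, with no added patients, visits or data.

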Once 50% of total enrollment is reached, the proportion of each arm with either acute rejection or subtherapeutic tacrolimus trough levels will be compared. If there is a significant difference (p < 0.05) between the two arms in terms of rejection or sub-therapeutic tacrolimus trough (level < 8), the PI and co-PI may choose to terminate the study early.

11) Withdrawal of Subjects

Discontinuation criteria from study for individual subjects:

Page

- Subject develops allograft loss (as defined by subject death, re-transplantation, transplant nephrectomy, or return to dialysis) within the period of their study participation
- Subject develops unacceptable toxicity or is withdrawn at the discretion of the patient's supervising physician
- Subject is lost to follow-up despite reasonable efforts by the investigator to locate the subject
- Subject withdraws consent for further treatment or expires during the course of the study
- Subject begins taking any prohibited medications
- Subject develops a severe neurologic condition (ie stroke, neurologic injury, blindness, or other incapacitating event) that prevents further neurocognitive testing during the period of their enrollment in the study.
- Conversion to a non-tacrolimus-based maintenance regimen in either study arm if required to
- manage toxicities
- With regard to patients receiving Envarsus, an inability to maintain a tacrolimus trough concentration >8 ng/mL for > 2 consecutive weeks during the course of the study, or conversion to twice-daily, immediate-release Tacrolimus
- With regard to patients receiving immediate-release tacrolimus, an inability to maintain a tacrolimus trough concentration >8 ng/mL for > 2 consecutive weeks during the course of the study, or conversion to Astagraf XL or Envarsus.
- Patients meeting inclusion criteria at time of randomization and not initiated on Envarsus or immediate-release tacrolimus within 7 days of study enrollment will be classified as a recruitment failure and not included in the full analysis set (FAS) or per protocol set (PPS) analysis.

Individuals who were enrolled in the study and completed their initial neurocognitive assessment but were not able to complete their follow up assessment due to any of the above will still be included in the baseline testing results. These individuals' further clinical data will not be collected upon their termination from the study.

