Individuals who were initially randomized to the Envarsus study arm whose participation is terminated at any point after their study enrollment will be converted back to IR tacrolimus as per usual conversion dosing.

12) Risks to Subjects

This study poses minimal risk to subjects. Envarsus has equivalent rates of rejection compared with IR tacrolimus in large controlled trials so we do not anticipate subjects to be at any increased risk as a result of taking Envarsus. Subjects will, however, need to spend more time in transplant clinic undergoing the testing needed for the study. This may mean more visits to the transplant center for the duration of their participation in the study.

This study also poses an unlikely and minimal risk of breach of confidentiality. The risk of loss of confidentiality will be minimized by assigning a unique study ID number to the patient at the time of study entry. Study information stored by the research personnel at UCDMC, which may include name

Page 8

and medical record number, will be kept strictly confidential and only available to the principal investigator and trained staff assigned to this study. All information will be kept secure in locked file cabinets accessible only by research personnel.

13) Potential Benefits to Subjects

The study will provide each enrolled patient \$20 at the beginning and \$20 at the end to compensate them for the time and effort they spend participating in this study. There is a potential benefit for those patients randomized to the Envarsus if there are any improved neurocognitive side effects lessened by Envarsus as opposed to IR tacrolimus.

14) Multi-Site Research

N/A

15) Community-Based Participatory Research

N/A

16) Sharing of Results with Subjects

Results will not be shared with the subjects. The testing that is part of the study do not impact clinical care.

17) Prior Approvals

Funding from Veloxis will be obtained prior to conducting this study.

18) Provisions to Protect the Privacy Interests of Subjects

Only research personnel who are HIPAA trained will interact with patients or have access to their records. All patient interactions will occur in the privacy of dedicated exam and interview rooms that provide confidentiality. All subjects will be informed in advance (at the time of consent) of the types of questions we will be asking for the study and the information that we will be obtaining upon study follow up.

19) Compensation for Research-Related Injury

N/A

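### Section 11 makes leaving tacrolimus because of toxicity a reason for termination, then sends every terminated Envarsus subject back to IR tacrolimus

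*Combined protocol and SAP*

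**What the plan says.** Three parts of Section 11 (Withdrawal of Subjects) in the combined protocol and SAP bear on this.

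- **The list of discontinuation criteria.** One entry is "Conversion to a non-tacrolimus-based maintenance regimen in either study arm if required to" manage toxicities. Another is "Subject develops unacceptable toxicity or is withdrawn at the discretion of the patient's supervising physician". The list also covers allograft loss, loss to follow-up, death, and withdrawal of consent to continued treatment.
- **The paragraph after the list.** It concerns subjects who had the baseline tests but miss the follow-up tests for any listed reason. It calls this their termination from the study and says that their clinical data are not collected from then on.
- **The last paragraph.** It defines its population as "Individuals who were initially randomized to the Envarsus study arm" and says of those "whose participation is terminated at any point after their study enrollment will be converted back to IR tacrolimus as per usual conversion dosing".

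Neither Section 11 nor any other part of the document makes an exception by reason for termination.

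**The concern.** One provision recognises that a subject may have to leave tacrolimus because of toxicity, and ends participation for that reason. The other then prescribes tacrolimus for the same subject. Site staff who turn to the protocol at that moment find an instruction that reverses the decision that triggered it.

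The population makes this worth correcting. Subjects are kidney recipients aged 65 or older, enrolled by 8 weeks after transplantation (Sections 4 and 7). Adverse-event monitoring lasts only as long as participation does (Section 10), and clinical data collection stops at termination (Section 11). If the instruction were applied, the study would not record what followed.

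**Working it through.** No arithmetic applies. The check sets the last paragraph of Section 11 against the list above it.

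**Step 1. Do the listed reasons count as termination?** Yes. The paragraph between the list and the final instruction uses that word for subjects who leave for any listed reason before follow-up.

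**Step 2. Whom does the instruction cover?** It covers subjects by assigned arm, not by the drug they take when they leave. Its timing is unrestricted, its verb is mandatory, and no clause limits it to cases where it is clinically suitable.

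**Step 3. Can it be followed for each reason?**

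| Reason in the list | Instruction to return to IR tacrolimus |
|---|---|
| Switch to a regimen without tacrolimus for toxicity (either arm) | Direct contradiction |
| Death; loss to follow-up | Cannot be carried out |
| Graft loss other than death (for example nephrectomy or dialysis) | Unqualified; possible conflict |
| Unacceptable toxicity, or the supervising physician's discretion | Unqualified; possible conflict |
| Withdrawal of consent to continued treatment | Unqualified; possible conflict |
| Envarsus subject already moved to twice-daily IR tacrolimus | Consistent, and redundant |
| Envarsus subject unable to hold a trough above 8 ng/mL; prohibited medication; severe neurologic condition | No contradiction on the text |
| Assigned drug not started within 7 days | Nothing to convert from if Envarsus was never begun |

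The remaining entry, on troughs and conversions among subjects receiving IR tacrolimus, lies outside the instruction.

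**Step 4. Does anything elsewhere qualify it?** Three places might, and none does.

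- Section 7, step 6: Envarsus subjects are "given the option to remain on Envarsus or return to IR tacrolimus", but only once the study period is over.
- Section 7, step 4: clinical judgement governs dose adjustment towards the target trough. It is not tied to what happens at termination.
- Section 11: the supervising physician's discretion is a ground for withdrawal. It is not a rule for treatment afterwards.

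The result is one strict contradiction, two situations in which the instruction cannot be carried out, and three entries where it may conflict with the reason for leaving.

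**The case against.** The strongest defence is that the sentence presupposes a subject who is still taking Envarsus. Converting someone back at the usual conversion dose needs a current Envarsus dose, and a subject already moved to another regimen has none. The usual post-transplant team manages these patients and is unlikely to restart a drug it has just stopped. This is plausible as intent, and it makes forced re-exposure unlikely in practice. It lowers the severity. It does not remove the contradiction, because the sentence selects subjects by original assignment and states no such limit.

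The second defence concerns the other reasons, and it largely stands. Unacceptable toxicity is listed separately from the switch off tacrolimus, so it need not mean that tacrolimus must stop. Section 7 describes IR tacrolimus as the current standard of care, supplied through the patient's insurance. Returning to it after consent is withdrawn can be read as the end of study treatment rather than a new study intervention. A reader might infer that the instruction directly contradicts four or more listed reasons. The text supports one, and the others are infeasible or only possible conflicts.

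**Conclusion.** The point holds in a limited form. Section 11 contradicts itself for an Envarsus subject who is terminated because tacrolimus was stopped for toxicity, and the final instruction is wrong as written for that subject. Severity is moderate. The endpoints, the t test, the sample size and the collected data are unaffected. The conclusion rests on the wording alone.

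The number of subjects affected is unknown. A reader might apply an assumed all-cause termination rate of 5% to 15% to the 30 subjects planned for Envarsus, giving 30 × 0.05 = 1.5 to 30 × 0.15 = 4.5. That range counts every termination. The contradiction reaches only those moved off tacrolimus, a subset whose size the documents do not give.

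Four stronger inferences are tempting, and the documents do not support them:

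- **Confounded safety comparison.** Clinical data collection ends at termination, so events after the drug change do not enter the dataset and cannot confound it.
- **Contradiction for stroke or neurologic injury.** Section 3 links peak levels to toxicities such as tremor and builds the trial's hypothesis on that link. It does not mention stroke or injury. That discontinuation criterion is framed around the subject being unable to complete further testing.
- **Unequal treatment of the arms.** Subjects on IR tacrolimus ordinarily have nothing to be converted back from, so an instruction for the Envarsus arm alone is natural.
- **Conflict with the choice in Section 7, step 6.** That step covers subjects who complete the study period, a different group from those terminated.

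**What to change.** The sponsor and investigators should reconcile the last paragraph of Section 11 with the list of discontinuation criteria. The revised paragraph should state to which termination reasons the return to IR tacrolimus applies, to which it does not, and which role decides in an individual case. It should deal expressly with the switch off tacrolimus for toxicity, where the passages now contradict each other, and with death and loss to follow-up, where the instruction cannot be carried out. It should also say how it stands for unacceptable toxicity, graft loss and withdrawal of consent. What treatment follows in each case is for the transplant team and is not proposed here.

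The cost is one reworded paragraph by amendment. No patients, visits or data are added, and the analysis does not change.
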